12. AVAILABLE ALTERNATIVE TREATMENTS

There are no available alternative treatments as this is not a treatment study. If subjects express the desire for treatment, they will be given referrals for treatment and not be allowed to participate in this study.

13. RESEARCH MATERIALS, RECORDS AND PRIVACY

Urine and blood samples will be collected at screening prior to a subject's participation in the experimental protocol under another IRB approved protocol (#44379). These urine samples will be tested for the presence of a full range of drugs of abuse. Blood samples will be used for the laboratory chemistries. Females will also be given a pregnancy test at the time of screening (via the urine sample). Urine drug and pregnancy tests will be conducted prior to the conduct of each experimental session. Other data obtained from the subjects will involve subjective effects based on questionnaires, various computer-based tasks and non-intrusive staff observations and ratings. The consent form states that subject's confidentiality will be protected.

14. CONFIDENTIALITY

Identifying information will be stored in a separate, locked area from all other de-identified data and codes linking the two will be kept under lock and key or on password protected computers. Incidental materials containing subject identifiers will be shredded or incinerated. Identification and access of identified data/specimens will be available only to study investigators when it is detrimental to subject safety or the conduct of the research protocol. For example, if a subject has an adverse event, we will want to obtain a quantitative drug screen to identify whether there may have been illicit drug use while in the study versus a true adverse event related to the study procedures. In the future, data/specimens may be shared with non-UK affiliations in a HIPAA compliant manner.

15. PAYMENT

Subjects will be paid \$60 for each day they reside on the CRU and will receive a \$60 completion allowance for these days if they complete the entire experiment. Subjects may also earn additional payment during study sessions in the self-administration procedure (up to \$30/session, \$360 total). The amount earned by the subject will be disbursed to them upon completion of the study. Payments will be disbursed in amounts up to \$500 dollars and will be given once per week following discharge until the subject is paid in full. When subjects return on a weekly basis to receive their payments, we will survey them regarding their drug use since being discharged from the study. A subject can earn approximately \$4,320 for participating in the study.

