5-7	Experimental Sessions 1-3. Subjects complete 1 sample and 5 choice trials to receive cocaine (0, 10 and 30 mg/70 kg) or money (\$6.00) by responding on the concurrent progressive-ratio schedule. Assessment battery completed following administration of the sampling dose as described below.
8-9	Washout. Placebo administered twice daily (0700 and 1900 hours).
10-15	Zolmitriptan (2.5 mg/day) maintenance. Administered in divided doses (0700 and 1900 hours).
13-15	Experimental Sessions 4-6. Details are the same as for days 5-7.
16-17	Washout. Placebo administered twice daily (0700 and 1900 hours).
18-23	Zolmitriptan (5 mg/day) maintenance. Administered in divided doses (0700 and 1900 hours).
21-23	Experimental Sessions 7-9. Details are the same as for days 5-7.
24-25	Washout. Placebo administered twice daily (0700 and 1900 hours).
26-31	Zolmitriptan (10 mg/day) maintenance. Administered in divided doses (0700 and 1900 hours).
29-31	Experimental Sessions 10-12. Details are the same as for days 5-7.
32	Discharge.
Note	Dosing order is illustrative. All doses will be administered in random order.

This experiment will require each subject to participate for approximately one month. Experimental sessions will be conducted as outlined in Table 1 above. We would like to note four important points relating to the table above: 1) To avoid experimental testing on weekends, subjects may be maintained on zolmitriptan or placebo for longer than outlined above (i.e., maintenance conditions may last for two days longer than in the example above). 2) The order of zolmitriptan maintenance conditions and cocaine experimental sessions will be randomized. 3) All maintenance conditions will be followed by a two-day washout period in which the participant receives a placebo delivered in a double-blinded fashion. 4) If subjects leave the protocol for a reason unrelated to study procedures (e.g., a family emergency or dental problems), they may be re-admitted

with physician approval to complete the remainder of the protocol, picking up in the condition where they left off (i.e., sessions/dose conditions that have already been completed will not be repeated). Thus, they may not complete the protocol over one approximately 33-day admission but can complete the protocol over two admissions totaling approximately 33 days.

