Cardiovascular Measures and Body Temperature. Heart rate, blood pressure, cardiac rhythmicity (i.e., electrocardiograms [ECG]) and body temperature will be recorded before cocaine administration and at frequent intervals after dose administration. Cardiac rhythmicity (i.e., electrocardiograms [ECG]) will be recorded for 30 minutes before intravenous cocaine administration and continuously during each experimental session. No drugs will be administered if a subject's heart rate is \geq 90 bpm if systolic pressure \geq 140 or diastolic pressure \geq 90 mmHg. A subject will be excluded from further participation if at any time he or she exceeds our cardiovascular safety and tolerability thresholds (i.e., heart rate above 130 bpm, diastolic pressure increases above 120 mmHg or systolic pressure above 180 mmHg or clinically significant ECG changes) after administration of zolmitriptan alone, cocaine alone or cocaine-zolmitriptan combinations. Heart rhythmicity will be assessed via 3-lead telemetry continuously during each experimental session, will be printed out and verified as normal prior to dose administration, and will be monitored continuously for a minimum of 15 minutes following each infusion.

Safety and tolerability outcomes: Udvalg for Kliniske Undersøgelser (UKU). The UKU is a standardized, validated rating scale that assesses over 50 potential side effects (e.g., sedation, akathisia, weight change) associated with administration of centrally acting drugs (Lingjaerde et al., 1987). It also includes a global assessment of how these side effects interfere with functioning. This questionnaire will be completed daily at 1630 h. We have routinely used this scale to evaluate the safety and tolerability of maintenance doses and cocaine ([name] et al., 2008; [name] et al., 2009; [name] et al., 2007; 2008; 2016). A subject will be excluded from further participation if at any time he or she exceeds adverse event safety and tolerability thresholds (i.e., an effect rated as severe lasting more than 24 h) after drug administration.

Drug Dose and Administration. All drugs will be administered under double-blind conditions and medical supervision in randomized order. We currently hold an IND for intravenous cocaine administration and will modify it to test intravenous cocaine during zolmitriptan maintenance. To maintain the blind, only [name] and the Investigational Drug Service will have access to dose conditions for subjects.

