As described above, Drs. [name], [name], and [name] will screen all potential subjects for physical and psychiatric contraindications to participation. Urine samples will be monitored throughout each study to ensure that female subjects are not pregnant and that all subjects are adhering to the drug use restrictions. All subjects in these studies will be thoroughly informed of the various drug side-effects which they might experience and will be appropriately cautioned concerning their activities in the hours after drug administration. However, this should not pose a significant problem because research subjects will always be under the direct supervision of the nursing staff on the CRU during drug dosing. Participation is voluntary, so individuals can withdraw at any time if they find the behavioral procedures or drug effects undesirable. The drug doses to be administered in the present experiments were chosen to minimize, if not eliminate, the chance of these side effects occurring. As noted above, Drs. [name], [name], and [name] will screen all potential research subjects for medical contraindications, and [name] of the University of Kentucky Gill Heart & Vascular Institute will review the ECG, prior to study participation. Drs. [name], [name], and [name] will monitor research subjects throughout their participation. We anticipate that careful subject selection, dose selection and subject monitoring will greatly reduce, if not eliminate, the occurrence of serious side effects. The assembled team of investigators has been conducting inpatient and outpatient human behavioral pharmacology studies with healthy subjects and subjects with histories of drug abuse for more than 60 years combined and have never observed a serious drug-related unanticipated serious adverse event. To monitor for adverse events/side effects, the UKU Side Effects Rating Scale will be completed daily with subjects by CRU nursing staff. Staff observations, subjective-effects drug effects and spontaneous subject report will also be used to monitor for adverse events.

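### Half of residence pay depends on finishing the study, with no stated exception for subjects whom the investigators remove for safety

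*Combined protocol and SAP*

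**What the plan says.** **Payment (section 15).** "Subjects will be paid \$60 for each day they reside on the CRU". A second $60 per day is a "completion allowance for these days if they complete the entire experiment". Choice-task earnings come on top ("up to \$30/session, \$360 total"), and the total is summarised as "A subject can earn approximately \$4,320 for participating in the study". The section does not mention removal by the investigators.

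**Removal.**
- Section 7, on the UKU side-effect scale, excludes a subject who has "an effect rated as severe lasting more than 24 h".
- Section 10 dismisses subjects with significant abstinence symptoms after admission, and stops participation for those who become overly distressed.
- Sections 7 and 10 also exclude on heart rate, blood pressure and ECG findings.

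**How harm is detected.** Section 10 has nursing staff complete the UKU with the subject each day. It adds: "Staff observations, subjective-effects drug effects and spontaneous subject report will also be used to monitor for adverse events". It also offers voluntary exit as a protection: "individuals can withdraw at any time if they find the behavioral procedures or drug effects undesirable".

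**Re-admission (section 7).** A subject who leaves for a reason that has nothing to do with the study procedures may return, with physician approval, and finish over "two admissions totaling approximately 33 days". No such route is described for a subject removed because of a drug effect.

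**Analysis (section 7, Data Analysis).** Only completers are analysed. UKU items go into a repeated-measures ANOVA with zolmitriptan dose and day as factors.

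**The concern.** The allowance is large, and on the plain wording it is lost in full by anyone who does not finish, whatever the reason. Several exits meant to protect subjects rest partly on what the subject tells staff. A subject who honestly describes a severe, lasting effect would give up half the residence pay already built up. One who plays the effect down would keep it.

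The first thing at stake is subject safety: a subject with an unreported severe effect stays in and receives further doses, although the protocol's own rule would have ended participation. The second is the quality of the reported side-effect information, which section 17 classes as tertiary. The documents give no reason to think that the primary break-point outcomes are affected through this route.

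**Working it through.** **Inputs.** Residence pay $60 per day, allowance $60 per day, session earnings up to $360 and the stated total of about $4,320 (section 15). Stay of about 33 days (section 7; Table 1 runs from day 0 to day 32). Enrolment of 30 for 20 completers (section 4).

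**1. Reproduce the plan's total, and settle what the allowance is.**
- Allowance paid per day: 33 × $60 + 33 × $60 + $360 = $1,980 + $1,980 + $360 = $4,320. This matches exactly.
- A single $60 bonus: $1,980 + $60 + $360 = $2,400. This does not match.
- Per-day allowance over 32 or 34 days: $4,200 or $4,440.

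The stated total fits a per-day allowance over 33 days.

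**2. Size of the allowance.** $1,980 / ($1,980 + $1,980) = 50% of residence pay. $1,980 / $4,320 = 45.8% of the maximum.

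**3. What a removed subject loses on the plain wording.** After *r* resident days, accrued allowance lost = 60 × *r*. Future residence pay and allowance lost = 120 × (33 − *r*). Session earnings are left out.

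| Days resided | Accrued allowance lost | Future pay lost | Allowance as share of combined loss |
|---|---|---|---|
| 8 | $480 | $3,000 | 480 / 3,480 = 14% |
| 16 | $960 | $2,040 | 960 / 3,000 = 32% |
| 24 | $1,440 | $1,080 | 1,440 / 2,520 = 57% |
| 32 | $1,920 | $120 | 1,920 / 2,040 = 94% |

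The allowance lost always equals half of the residence pay accrued. It becomes the larger part of the combined loss once 60*r* exceeds 120(33 − *r*), that is, after day 22.

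**4. Which exits the incentive can reach.** Partly dependent on subject report: the UKU rule, abstinence symptoms, distress, and voluntary withdrawal because of drug effects. Not dependent on it: heart rate, blood pressure and ECG limits, which are measured.

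**5. Effect on the analysed UKU scores.** Take a subject with a severe effect lasting more than 24 hours.
- Honest report: the subject is excluded, does not complete, and contributes nothing to the ANOVA.
- Played-down report: the subject stays, may complete, and contributes a lowered score.

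Compared with the true experience of all dosed subjects, both paths lower the analysed scores. Compared with the data set that honest reporting would give, playing down can raise the mean, because a lowered score may still exceed the average completer's. The direction depends on the comparison, and the documents give no rate of severe effects or of under-reporting. The effect can be neither sized nor signed.

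**The case against.** **Forfeiture is read from silence.** Section 15 never says that a subject removed for safety loses the allowance, and the consent form, which may deal with it, was not available for this review. That stands, so the point cannot be put as a proven forfeiture. But section 15 sets an unqualified condition. If the consent form differs, the two need aligning; if it does not, the gap is real.

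**Reporting is not left to the subject alone.** Nurses complete the UKU with the subject, staff observe independently, and the cardiovascular triggers are measured. This stands and limits the point to subject-reported effects. It does not remove it: nausea, chest pain or neck pressure, all listed in section 9, are known largely because the subject mentions them.

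**The UKU rule may seldom apply.** Section 9 says side effects usually pass within 24 hours, and the rule needs a severe effect lasting longer. Abstinence symptoms would probably appear early, when little allowance has accrued. Both limit how often the incentive matters.

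**A reader might infer that the safety ratings are biased downward.** The documents do not support this as a finding. They show an incentive, not behaviour, and step 5 shows that even the direction is open under a completers-only analysis. An assumed rate of under-reporting would not give a usable estimate either, since the planned UKU analysis is an ANOVA of item scores and not a comparison of severe-effect incidence.

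**The remedy is partial.** A subject removed after 16 days would recover $960 of a combined $3,000. This stands.

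**Conclusion.** The point holds as a gap in the payment terms with a bearing on subject safety. As written, $1,980 of a possible $4,320 depends on completion with no safety exception, while some safety removals depend partly on what the subject reports. The consequence is an incentive to under-report and a risk, of unknown size, of continued dosing after the protocol's own rule should have ended it. No bias in the side-effect results is shown.

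This rests on two assumptions: that section 15 is applied as worded, and that the stay is about 33 days. Section 7 allows each of the four maintenance conditions to run two days longer. The dollar amounts would then rise (up to 33 + 8 = 41 days, an allowance of $2,460), but the 50% share of residence pay would not change.

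The point is worth acting on because the correction is cheap, not because a study conclusion is in doubt. The completers-only rule is a separate and more direct limit on the UKU analysis; reporting safety data for all dosed subjects would address it.

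**What to change.** In section 15 and the consent form, state that a subject whom the investigators remove for a safety reason confirmed by the study physician keeps the $60 allowance for each day already resided. If the consent form already says something different, align the two. Tell subjects this at consent, since an exception they do not know about cannot change what they report. Also state whether a subject who withdraws because of drug effects counts as a safety removal, because section 10 presents that exit as a safeguard.

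**Cost.** One sentence in each document. On a 33-day stay the payment is at most 32 × $60 = $1,920 per subject so removed. If all 30 − 20 = 10 planned non-completers were safety removals at day 16 (an assumption), the total would be 10 × 16 × $60 = $9,600, against a maximum of 20 × $4,320 = $86,400 for the completers. Section 10 reports two cardiovascular exclusions in 20 years of cocaine studies, which suggests a lower figure, although that count does not cover the report-based triggers.

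**Downside.** A subject who wants to leave gains some motive to exaggerate an effect and keep the allowance. Physician confirmation limits this, as does the loss of $120 for each remaining day. That same loss means the incentive to under-report is reduced and not removed, most noticeably early in the stay. No dose, threshold or removal rule changes.

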16. COSTS TO SUBJECTS

There will be no cost to the subject for participating. Costs for the screening procedures (i.e., medical history questionnaire, physical examination including laboratory chemistries (blood chemistry screen, complete blood count, urinalysis) and a psychiatric examination will be paid by the Laboratory of Human Behavioral Pharmacology. Grants funded by the National Institutes of Health have no mechanism to pay for research-related injuries.

17. DATA AND SAFETY MONITORING

Data Monitoring Plan

Data will be collected using a computerized data collection and management system wherever possible. This system automates the collection of data, which ensures the accuracy and completeness of data collection. The data are stored in a unique file on the hard drive of the computer and are printed after all the tasks are completed. In all instances, the data files do not contain the name of the subject, but instead, a unique four-digit number identifies each subject. A computer file linking the unique number with the subject's name will be kept on a stand-alone, password-protected computer. All data requiring hand entry (e.g., cardiovascular measures) will be double entered by two separate staff members and comparison macros run to ensure accuracy. Data files for experimental tasks and physiological measures from each experimental session will be manipulated and combined into a single electronic spreadsheet for each subject by the PI. Data for all subjects will then be combined into a single electronic spreadsheet and separated by experimental measure for statistical analysis.

The primary outcomes will be the break points for drug and money in the cocaine self-administration task, analyzed as a function of zolmitriptan maintenance conditions. Secondary outcome measures will be abuse-related subjective and cognitive effects of cocaine, analyzed as a function of zolmitriptan maintenance conditions. Tertiary outcome measures will be the physiological and side-effects of cocaine, analyzed as a function of zolmitriptan maintenance conditions. Data will be analyzed using repeated measure ANOVA. The alpha level will be set at 5%.

As noted above, wherever possible, data are collected using an automated computer system, which increases the accuracy and completeness of data collection and ensures the validity and integrity of the data. The initial data manipulation described above will be conducted twice and compared. The quality of manipulated data and data analyses will be monitored by random inspection by the PI and/or Co-Investigators.

Safety Monitoring Plan

Potential subjects will provide information regarding their drug use history and undergo an extensive physical and psychiatric health screening to determine their eligibility and safety of their participation. Potential subjects must meet DSM-5 criteria for cocaine use disorder and must present with a urine sample positive for cocaine at the time of screening. Any potential subject with a history of clinically significant physical disease, current physical disease (e.g., impaired cardiovascular functioning, histories of seizure, asthma, diabetes, head trauma or CNS tumors) or current or past histories of psychiatric disorder, other than substance abuse or dependence, will be excluded from research participation. Females must be using an effective form of birth control to participate and must not be pregnant. Methods for monitoring adverse events (AEs) will include observations by the medical and research staff, spontaneous report by the subjects, regular measurement of physiological indices and use of the UKU Side Effects Rating Scale and subjective measures. Subjects will not receive study drug if they have any signs or symptoms that may contraindicate its administration (e.g., heart rate and blood pressure outside of predetermined range for a prolonged period, development of serious side effects).

All AEs occurring during the study will be collected, documented, and reported to the PI. The occurrence of AEs will be assessed for the duration of participation and during the follow-up visit at 1-month following study completion. Each week a study investigator will review the AE forms from the previous week for events that were reported as new or continuing. The study investigators will follow all AEs to the point of a satisfactory resolution. Subjects may be withdrawn from the study if the medically responsible investigator determines it is the best decision to protect the safety of the subject. All AEs will be assessed to determine if they meet criteria for a serious adverse event (SAE).

Serious Adverse Events, as defined by the FDA, will be systematically evaluated for the duration of participation and during the follow-up visit at 1-month following study completion. If there is an SAE that is continuing, we will schedule special visits with those subjects at 3- and 6-months post-discharge. Any SAE, whether or not related to the study drug, will be reported to the IRB, NIDA, and the FDA. The initial SAE report will be followed by submission of a completed SAE report to all three institutions.

If a subject either withdraws from the study or the investigator decides to discontinue a subject due to an SAE, the subject will have appropriate follow-up medical monitoring. Monitoring will continue until the problem requiring hospitalization has resolved or stabilized with no further change expected, is clearly unrelated to the study drugs or results in death. Outcome of SAEs will be periodically reported to IRB, CRU, NIDA and the FDA. A summary of the SAEs that occurred during the previous year will be included in the annual progress report to NIDA, the IRB, CRU, and FDA.

